5.1 Type of study

Descriptive multicenter cross-sectional study.

5.2 Study population

All persons over 18 years of age who are treated in the included health care institutions (IPS) and who are users of hospitalization, emergency, outpatient and any other hospital care services.

5.3 Inclusion criteria

Have at least one of the following risk factors for hepatitis C.

- Over 50 years of age with no risk factors.
- Over 18 years old and < 50 years old, with risk factors for hepatitis C:
 - ✓ Persons who have received medical or dental interventions in health care settings.
 - ✓ Persons who have had tattoos, body piercings, or scarification procedures.
 - ✓ Persons with HIV or hepatitis B infection.
 - ✓ Persons who inject drugs.
 - ✓ Persons who have used intranasal drugs.
 - ✓ Persons deprived of liberty and previously incarcerated persons.
 - ✓ Anyone with abnormal liver tests or liver disease.
 - ✓ Students, health care workers, or members of public safety (e.g. correctional

service officers or police) who have come into contact with blood at work through needlestick or sharps injuries.

- ✓ Anyone who has undergone hemodialysis.
- ✓ Persons who received transfusions in Colombia before 1996.
- ✓ Persons with comorbidities potentially associated with CH: diabetes, ischemic heart disease, cryoglobulinemia, chronic renal failure, Sjögren's syndrome, hypothyroidism, lichen planus, rheumatoid arthritis, HIV, non-Hodgkin's lymphoma, acute lymphoblastic leukemia, waldenstrom's macroglobulinemia.
- Individuals previously treated for HCV with sustained viral response in whom reinfection is suspected (individuals who continue to engage in risk behaviors)
- Accept to participate in the study by signing the informed consent form.

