the high-cost account (including those in the 2017-2018 cohort). Of the 634 users enrolled in the 2019 cohort, 584 initiated treatments, of which 97.6% (570) did so with centrally purchased drugs. Of the 326 cases included in the 2020 cohort, 219 initiated treatments, 98.6% (216) with centrally purchased drugs, which made evident the almost exclusive use of the strategy, except in cases of stage 4-5 chronic kidney disease. Of the 1,142 patients reported to the CAC in 2017 and 2018, 1,079 had initiated treatment and of these 84.2% (n=909), were included in the centralized purchasing model, the most frequently used treatment in 98.2% of cases in the 2019-2020-2021 cohort was sofosbuvir/velpatasvir, reaching 98.77 in 2021 (12).

Regarding the effectiveness of the treatment, it was found that for the 2017-2018 cohort, with centrally purchased drugs, the effectiveness was 95.1% and with drugs outside the centralized purchasing model it was 96.4%. For the 2019 cohort, the effectiveness was 98% and 100% respectively. In the 2020 cohort, treatment effectiveness is at 100% (12).

The report concludes that there is high effectiveness of direct-acting antiviral treatments (greater than 95%), follow-up is observed in the application of the clinical route and practically exclusive use of drugs included in the centralized purchasing model; however, there is a need to encourage screening in the population over 50 years of age and according to risk exposure, as established in resolution 3280 of 2018 (12).

3 Research question

What is the prevalence of HCV in the population with risk factors for hepatitis C virus infection captured by screening with rapid tests in health care institutions in Colombia?

4 Objectives

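### The study asks about people with risk factors but also admits over-50s without any; no split by factor status is planned, and the data form cannot fully support one

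*Combined protocol and SAP*

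**What the plan says.** **Target population.** Section 3 asks "What is the prevalence of HCV in the population with risk factors for hepatitis C virus infection captured by screening with rapid tests". The introduction, section 4.1, the sample-size rationale in section 5.8 and the first indicator in section 7 use the same population.

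**Eligibility.** The opening line of section 5.3 is "Have at least one of the following risk factors for hepatitis C". Its first item is "Over 50 years of age with no risk factors" and its second is "Over 18 years old and < 50 years old, with risk factors for hepatitis C", followed by a list of factors. That list includes "Persons who have received medical or dental interventions in health care settings", with no further qualifier. A separate route admits "Individuals previously treated for HCV with sustained viral response in whom reinfection is suspected".

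**Analysis.** Section 5.10 plans frequencies, percentages, summary statistics for continuous variables, and exploratory chi-square tests of sociodemographic variables and risk factors against antibody positivity. It plans no prevalence by entry route or by any factor versus none.

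**Data.** Table 1 in section 5.5 defines one yes/no comorbidity variable that names 11 distinct conditions (two are listed twice). Section 5.11 names Annex 1 as the collection form.

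**The concern.** Unless sections 4.1 and 5.3 are reconciled, the headline percentage pools people with a factor and people whom the protocol itself describes as having none. Their proportions would be set by convenience recruitment (section 5.7). A reader could then take the figure as the prevalence in a risk-factor population when it describes eligible hospital users more broadly.

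The form limits repair afterwards. An over-50 whose only factor has no field on Annex 1 looks the same as an over-50 with no factor. The comorbidity variable, which feeds a planned chi-square test, would be wrongly coded for some participants. Information not asked at screening may not be recoverable later.

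**Working it through.** **1. The age wording**

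- The opening line of 5.3 requires at least one listed factor; the first item describes people with none. Treating age over 50 as the factor removes the conflict, but the protocol does not say so.
- The theoretical framework reports that "there is a need to encourage screening in the population over 50 years of age and according to risk exposure". This supports screening over-50s, but it names age and exposure as two grounds.
- Read literally, the two age items give no age-based route to someone aged exactly 50, or to someone over 50 who has a factor.

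**2. Section 5.3 and Table 1 (section 5.5) against Annex 1**

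| Item | Field on Annex 1 |
|---|---|
| Suspected reinfection after prior treatment | None |
| Listed comorbidities | Partial: diabetes, cryoglobulinemia, coronary artery disease, renal failure |
| Medical or dental intervention | Partial: major surgery, hemodialysis, pre-1996 transfusion |
| Occupational blood exposure | Present, but 5.3 begins "Students, health care workers, or members of public safety" and the form omits students |
| Tattoo, piercing, scarification | Present, but scarification is not in the wording |

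For the comorbidity variable, 11 − 4 = 7 conditions have no field: Sjögren's syndrome, hypothyroidism, lichen planus, rheumatoid arthritis, non-Hodgkin's lymphoma, acute lymphoblastic leukemia and Waldenström's macroglobulinemia. Counted by 5.3 criterion, one has no field and two are partly captured. In the other direction, men who have sex with men is a Table 1 risk factor that 5.3 does not list.

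**3. The plan's own figure**

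Section 5.8 gives n = DEFF·N·p(1−p) / [(d²/Z²)(N−1) + p(1−p)]. With N = 280,186, p = 0.5, d = 0.05, DEFF = 3 and Z = 1.96, this returns 1,150.86, so the stated 1,151 per institution reproduces. It is sized for one pooled group, with no allowance for a split.

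**4. How much the mix could matter (illustration)**

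Assumptions:
- Prevalence is 0.67% in over-50s with no factor. This is the national figure in the introduction; applying it here is an assumption.
- Prevalence r is 1%, 2% or 5% in people with a factor. The 2% and 5% echo general-population seroprevalence thresholds in the introduction; they are not risk-group estimates. The protocol does not say whether its 0.67% measures the same thing.
- A share s of participants has a factor.
- Total n = 7 × 1,151 = 8,057. The protocol gives only a per-institution minimum.
- The design effect of 3 applies to the total, so effective n = 8,057/3.

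Pooled prevalence = (1 − s) × 0.67% + s × r, with a Wilson 95% interval:

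| s | r = 1% | r = 2% | r = 5% |
|---|---|---|---|
| 20% | 0.74% (0.48–1.14) | 0.94% (0.64–1.38)* | 1.54% (1.14–2.08)* |
| 50% | 0.84% (0.55–1.26) | 1.33% (0.97–1.84)* | 2.83% (2.27–3.53)* |
| 80% | 0.93% (0.63–1.37) | 1.73% (1.30–2.30) | 4.13% (3.44–4.95)* |
| 90% | 0.97% (0.66–1.41) | 1.87% (1.42–2.45) | 4.57% (3.84–5.42) |

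\* The interval excludes r.

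In the first three rows 5 of 9 intervals exclude r, and the pooled value is 31% (1.536/5) to 93% (0.934/1) of r. At s = 90% none excludes it, and the same holds at 95% and 98%.

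The direction is also open. With 2% in over-50s with no factor and 1% in people with one, the pooled value is 1.8%, 1.5% or 1.2% at s = 20%, 50% or 80%, which is above the risk-group value.

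**5. Precision of the factor group alone**

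At a true 2% and design effect 3:

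| s | All seven institutions | One institution of 1,151 |
|---|---|---|
| 20% | n ≈ 1,611: 1.11–3.57% | n ≈ 230: 0.47–8.11% |
| 50% | n ≈ 4,028: 1.38–2.90% | n ≈ 576: 0.77–5.12% |
| 80% | n ≈ 6,446: 1.49–2.68% | n ≈ 921: 0.93–4.26% |

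**The case against.** The best defence is that 5.3 lists age over 50 first among its factors, so the item means only that no further exposure is needed, and every entrant then has a listed factor. That is a natural reading and may be what was intended. It turns the first part of the point into a request for clarification, but it does not remove the point, because the item's own words deny a risk factor.

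The second objection is that the medical or dental item is unqualified and every participant is a hospital user, so nearly everyone may have a listed factor. This stands. It makes shares of 90% or more plausible, and there the illustrated dilution is within sampling error.

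Third, the form already records age and many factors, so under-50s and over-50s can be separated now, and chi-square tests of the other single factors are unaffected. That is also right. What remains is the comorbidity variable and the split among over-50s.

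Finally, section 5.9 describes a tablet data-capture form that is not reproduced apart from Annex 1. If it already holds the missing fields, only the annex needs updating.

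A reader might infer that the pooled figure will understate the prevalence in people with risk factors, or that over-50s should not be enrolled. The protocol supports neither: it gives no prevalence by factor status and no expected mix, and it offers a rationale for screening over-50s.

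**Conclusion.** The point holds as an inconsistency in the target population together with a gap in the data form. Two parts rest on the text alone: the stated population and 5.3 do not agree as worded, and the comorbidity variable in section 5.5 cannot be completed from Annex 1. The size and direction of any effect on the pooled prevalence are unknown. The illustration shows that the effect could be material or negligible depending on the share with a factor, and every prevalence, share, total and pooled design effect in it is an assumption. The study remains valid as a description of eligible hospital users. Severity is minor to moderate.

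**What to change.** 1. **Form.** Add to Annex 1 one item for any other listed comorbidity (or the seven conditions separately), an item for suspected reinfection after prior treatment, and an item for medical or dental intervention. Add students and scarification to the wording of their existing items.
2. **Population.** Reconcile section 4.1 with 5.3 by stating whether age over 50 alone counts as a risk factor. Reconcile the two age items with each other, covering people aged exactly 50 and over-50s who have a factor.
3. **Analysis.** Keep the pooled estimate, labelled as prevalence in eligible hospital users. Add a descriptive table of prevalence with 95% intervals for people with at least one listed factor and for over-50s with none. Show the factor group again without people whose only factor is medical or dental intervention, since that item may leave few over-50s without a factor. State in advance how men who have sex with men and suspected-reinfection entrants are classified.

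**Cost.** Three to nine extra form items, two wording changes and one table, with no extra participants. It does need an amendment through the ethics committee of each institution and a change to the web data-capture application. Intervals in each stratum will be wider than the pooled one, especially within a single institution.

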4.2 Specific objectives

- Characterize the study population socio-demographically.
- Describe the epidemiological characteristics of HCV antibody-positive patients.

- Determine the proportion of patients with positive HCV antibodies and positive viral load (quantitative) for HCV.
- Perform an exploratory analysis of the association of positive cases and the different risk factors for HCV infection.
- Quantify how many HCV-positive individuals were able to access the management pathway and treatment.

5 Methodology

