5.10 Data Analysis Plan

Descriptive analysis will be performed for all variables of interest proposed in this study. Descriptive statistics (frequencies and percentages) will be estimated. For continuous quantitative variables, measures of central tendency (mean and median) and measures of dispersion (variance, standard deviation) will be estimated. Possible relationships between sociodemographic variables, risk factors, and documentation of positive HCV antibodies will be explored, for which a bivariate analysis will be performed using X² (chi-square) tests to explore the proposed associations. All analyses will be performed with Stata version 18.

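### Under-50s enter by having a listed risk factor and 5.10 then tests those factors unadjusted in the pooled sample, so a common weak exposure can look null or protective

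*Combined protocol and SAP*

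**What the plan says.** Section 5.3 opens with the requirement "Have at least one of the following risk factors for hepatitis C". Two main routes follow. The older group is described as "Over 50 years of age with no risk factors". The younger group is "Over 18 years old and < 50 years old, with risk factors for hepatitis C", followed by a list that includes injecting and intranasal drugs, tattoos or piercings, HIV or hepatitis B, imprisonment, hemodialysis, occupational blood contact and several comorbidities. Two items on that list matter especially here:

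- "Persons who have received medical or dental interventions in health care settings", which has no further qualifier. Section 5.2 defines the source population as "users of hospitalization, emergency, outpatient and any other hospital care services".
- "Anyone with abnormal liver tests or liver disease".

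One specific objective in 4.2 is to "Perform an exploratory analysis of the association of positive cases and the different risk factors for HCV infection". In 5.10 this becomes: "Possible relationships between sociodemographic variables, risk factors, and documentation of positive HCV antibodies will be explored". The only method named is a bivariate chi-square test. The section states no age stratification, no multivariable model and no caution about how participants were selected.

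Most of the entry factors are yes/no variables in Table 1 of 5.5 and in Annex 1. Medical or dental intervention is in neither; major surgery is the nearest item. Table 1 groups the comorbidities into one yes/no variable, and Annex 1 asks about only four of them (diabetes, cryoglobulinemia, coronary artery disease, renal failure).

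**The concern.** An under-50 participant without tattoos, say, had to qualify through something else on the list. The comparison group for tattoos is therefore not a group of ordinary hospital users. It holds more people who inject drugs, have HIV, are on dialysis or have been in prison than the source population does. If any of those factors strongly raises the chance of a positive antibody test, the unexposed group's positivity is inflated and the odds ratio for the weak factor is pulled down, possibly below 1. Adjusting for age alone does not help, because the distortion arises inside the under-50 stratum.

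Pooling the two age groups adds a second problem. Entry works differently on either side of 50, and both exposure frequency and HCV prevalence may differ by age, so a crude pooled comparison can also be confounded by age.

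At stake is the association objective in 4.2: a reported odds ratio could have the wrong sign, and a larger sample would only make the error look more certain.

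**Working it through.** **Plan's own figure.** No stated number is in dispute. For completeness, the per-institution sample size in 5.8 (p = 50%, d = 5%, design effect 3, N = 280,186) reproduces as 1,150.9, so 1,151, and does not depend on this point.

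**Inputs.** The entry rule and the test come from 5.3 and 5.10. The documents give no factor frequencies or factor-specific risks, so these are assumptions:

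- F, the share of under-50 attenders with some other listed factor: 15%, with 30% as a variant.
- Antibody positivity: 3% with another factor and 0.5% without. For scale, the background section cites a national prevalence of 0.67%.
- Factor X: no true effect (odds ratio 1) and independent of the others.
- q, the share of attenders with neither X nor another factor who still enter through the medical or dental criterion: 0 to 100%.

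**Formulas.** Everyone with X is eligible, so positivity in the exposed is F × 3% + (1 − F) × 0.5%. Those without X enter if they have another factor, or with probability q if they do not. Positivity in the unexposed is [F × 3% + (1 − F) × q × 0.5%] / [F + (1 − F) × q].

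**Worked case, F = 15%.** Exposed: 0.15 × 3% + 0.85 × 0.5% = 0.875%. Unexposed at q = 0: 3.0%. Odds ratio: (0.00875/0.99125) / (0.03/0.97) = 0.29. Unexposed at q = 50%: (0.45% + 0.2125%) / 0.575 = 1.152%, odds ratio 0.76.

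| q | Odds ratio, F = 15% | Odds ratio, F = 30% |
|---|---|---|
| 0% | 0.29 | 0.41 |
| 25% | 0.57 | 0.60 |
| 50% | 0.76 | 0.75 |
| 80% | 0.92 | 0.91 |
| 95% | 0.98 | 0.98 |
| 100% | 1.00 | 1.00 |

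**A fuller model.** This is an exact enumeration with seven independent factors and 0.5% risk with none. The assumptions are tattoo 25% (null), injecting 2% (odds ratio 20), HIV or hepatitis B 2% (5), prison 2% (4), intranasal drugs 5% (2), dialysis 1% (4) and comorbidity 12% (null).

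- Ignoring the medical or dental criterion, the crude odds ratio for the null tattoo factor in under-50s is 0.42; a true 1.3 appears as 0.54.
- With that criterion met by 25%, 50%, 80% and 95% of under-50s, the null factor shows 0.65, 0.80, 0.93 and 0.98.
- Pooled 50:50 with over-50s taken regardless of factors, again ignoring the criterion, it shows 0.68. With 7 × 1,151 = 8,057 participants, the chance of p < 0.05 is 40%.
- If no factor affects HCV, selection leaves the odds ratio at 1.00.

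**Age confounding from pooling alone.** Take equal numbers in the two strata, no entry selection, a null factor present in 40% of under-50s and 10% of over-50s, and positivity of 0.5% and 1.0% (all assumed). Exposed: (0.40 × 0.5% + 0.10 × 1.0%) / 0.50 = 0.60%. Unexposed: (0.60 × 0.5% + 0.90 × 1.0%) / 1.50 = 0.80%. The odds ratio is 0.75. With 25% instead of 40% it is 0.83.

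**Does adjustment work?** In the simple model, among people with another factor both arms have 3% positivity; among people without one both have 0.5%. The stratified odds ratio is therefore 1.00. In the fuller model, Mantel-Haenszel stratification on the other entry factors returns 1.00 for the null factor and 1.30 when the truth is 1.3.

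**The case against.** The strongest reply is that entry may hardly be selective at all. The medical or dental criterion is unqualified and the source population is hospital users. Read literally, it could admit nearly every under-50 attender, and at 80% to 95% the bias is already small (0.92 to 0.98). This stands as a limit on size. It does not dispose of the point, because the plan gives no frequency for the criterion and does not record it, so nobody could show afterwards that the bias was negligible.

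The analysis is also labelled exploratory, the study is descriptive, and the main prevalence objective is untouched. That is correct and limits the weight of the point, though the label does not remove a bias with a known direction. Over-50s dilute the selection effect in the pooled test, which is also correct, but pooling brings in age confounding. Finally, men who have sex with men and major surgery are analysed in 5.5 without being named entry factors, so the mechanism applies to most of the tested factors, not all.

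Three stronger readings are tempting and not supported:

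- **Entry necessarily creates false associations.** It does so only if entry is selective and another entry factor is related to HCV.
- **A factor would be wrongly dropped from hospital screening criteria.** The expected results and impacts in section 7 concern detection, linkage to treatment and dissemination. None proposes revising criteria from these tests.
- **Under-50 comparisons are uninterpretable and only over-50s should be tested.** Adjustment for the other entry factors largely removes the bias. Moreover, if "Over 50 years of age with no risk factors" is taken literally, the over-50 stratum has no exposed participants and could not carry the analysis.

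**Conclusion.** The unadjusted, pooled chi-square in 5.10 is not a sound way to meet the association objective given the entry rule in 5.3. In under-50s a truly null factor can show an odds ratio anywhere from about 0.3 to nearly 1. Where it falls depends mainly on how many people enter through the medical or dental criterion, which the documents leave unknown. Material bias is therefore possible but not demonstrated. All the figures rest on assumed frequencies and risks and on independent factors; the table describes under-50s alone, and the planned pooled test would mix this effect with age confounding.

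One part may resist correction. Abnormal liver tests or liver disease may be a consequence of HCV. Selection would then depend partly on the outcome, and adjustment might not fully remove the bias.

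This is a worthwhile, inexpensive improvement to an exploratory objective. It does not bear on the prevalence estimate or the sample size.

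**What to change.** In 5.10:

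- Do not pool the under-50 and over-50 strata for the association tests; analyse each separately.
- Within each stratum, adjust each factor for the other recorded entry factors by logistic regression or Mantel-Haenszel, in place of bivariate chi-square alone. Use a penalised fit if positives are few.
- Report under-50 associations as conditional on having an entry factor, and say so against the objective in 4.2.
- State that liver disease or abnormal liver tests may result from HCV, so some bias may remain after adjustment.

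In 5.5 and Annex 1, add the qualifying criteria not now captured: medical or dental intervention, and the comorbidities listed in 5.3 that the form does not ask about.

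In 5.3, clarify whether the over-50 wording means regardless of risk factors or only those without any. Over-50 associations can be estimated only under the first meaning.

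The cost is a few form fields and some rewording, plus less precise estimates because each stratum is smaller and adjustment uses up information.

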4.1 General objective

To determine the prevalence of HCV in patients with risk factors for HCV captured through opportunity screening in the hospital institutions included.

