5.5 Variables

Table 1. Study variables

Category	Variable name	Conceptual definition	Operational definition	Measuring scale
Sociodemographic	ID Number	ID Number	Personal identification number under which you are registered in the country of origin	Nominal
	Age	Duration of an individual's existence measured in units of time.	Number in years	Continual
	Gender	Categorizes the	1. Female	Nominal

Category	Variable name	Conceptual definition	Operational definition	Measuring scale
		individual according to her biological characteristics.	0. Male 2. Undetermined	
	Nationality	Country of birth	Name of country	Nominal
	Department of Residence	A geographic place to which the municipality or city where the person usually resides belongs.	Name of department	Nominal
	Municipality of residence	Geographic place municipality/city where the person usually resides.	Name of municipality/city	Nominal
	Health Service Provider Institution (IPS)	Place where the screening was performed.	1= Fundación cardioinfantil 2= Fundación Santafé 3= Clínica Colombia 4= Hospital Universitario San Ignacio 5= Fundación Valle de Lili 6= Hospital Pablo Tobón Uribe 7= Hospital Universitario Julio Méndez Barreneche E.S.E.	Nominal, polytomous
	Affiliation regime	Category of affiliation to the health system.	0=Not insured 1=Subsidized 2=Contributory 3=Special 4=Exception	Nominal, polytomous
	Entity Benefit plan administrator (EAPB) or Entity obliged to compensate (EOC)	The entity in charge of health care coverage.	Name of entity	Nominal
Risk Factors	Transfusion of blood products	Administration of hemocomponents before 1996.	0. No 1. Yes	Nominal, dichotomous

Category	Variable name	Conceptual definition	Operational definition	Measuring scale
	The year in which you received the transfusion	Date (year) in which you received the transfusion.	The year in which you received the transfusion	Continual
	Major surgery	Surgical procedure performed in the operating room under general or regional sedation that may require post-procedural in-hospital monitoring.	Abdominal laparotomy: 0. no; 1 Yes Gynecologic surgery of any type: 0. No; 1 Yes Orthopedic surgery of any type: 0. No; 1 Yes Any surgery that required in-hospital post-procedure surveillance for more than 24 hours: 0. 0. No; 1 Yes	Nominal, dichotomous
	Intravenous drug use	Having consumed intravenous drugs at any time.	0. No 1. Yes	Nominal, dichotomous

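### As worded, the two age routes in section 5.3 leave out people over 50 who have a listed risk factor, and leave age 50 unassigned

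*Combined protocol and SAP*

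**What the plan says.** Section 5.3 opens with the stem "Have at least one of the following risk factors for hepatitis C". Three clinical routes follow.

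- Older adults: "Over 50 years of age with no risk factors".
- Younger adults: "Over 18 years old and < 50 years old, with risk factors for hepatitis C". The list of exposures, infections and comorbidities is nested under this route only.
- Reinfection, with no age limit: "Individuals previously treated for HCV with sustained viral response in whom reinfection is suspected".

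The general objective in section 4.1 is "To determine the prevalence of HCV in patients with risk factors for HCV captured through opportunity screening in the hospital institutions included"; it sets no upper age. Table 1 in section 5.5 records age as "Number in years". Section 5.7 enrols eligible patients consecutively until the calculated size is reached. Section 5.10 plans bivariate chi-square tests of sociodemographic variables and risk factors against antibody positivity, and mentions neither stratification nor adjustment.

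**The concern.** An eligibility rule should give one answer for each patient, and that answer should match the objective. Here the older route requires the absence of risk factors, and the risk-factor route stops below 50. A 60-year-old on haemodialysis or living with HIV therefore has no age route, although such a patient clearly belongs in a study of prevalence among people with risk factors. The first item also sits badly with the stem, which asks for at least one risk factor and then lists having none.

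Two things are at stake. The first is whom the prevalence estimate describes: the literal rule gives younger people with risk factors plus older people without them. The second is what the exploratory risk-factor tests compare, because exposure to a listed factor would be confined almost wholly to one age group. If some of the seven hospitals follow the letter and others the likely intent, their prevalences would also differ for reasons unrelated to HCV.

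**Working it through.** **1. The plan's own figure.** Section 5.8 gives N = 280,186, p = 50%, d = 5%, design effect 3 and 95% confidence (Z = 1.96). The formula is n = DEFF × N × p(1 − p) / [d²/Z² × (N − 1) + p(1 − p)].

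- Numerator: 3 × 280,186 × 0.25 = 210,139.5.
- Denominator: 0.0025/3.8415 × 280,185 + 0.25 ≈ 182.59.
- n ≈ 1,150.86, which rounds up to the stated 1,151.

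Neither age nor risk-factor status enters the formula, so any repair of section 5.3 leaves 1,151 as it is.

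**2. The rule as logic.** Take age in completed years.

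- Route A: age > 50 and no listed factor.
- Route B: 18 < age < 50 and at least one listed factor.
- Route C: earlier sustained response with suspected reinfection, at any age.

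**3. Applying it to patients who are not suspected reinfections.** The last two columns replace route A with a more inclusive one.

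| Age | Listed factor | As written | A = over 50, with or without a factor | A = 50 or older, with or without a factor |
|---|---|---|---|---|
| 19 or 49 | yes | in | in | in |
| 19 or 49 | no | out | out | out |
| 50 | yes | **out** | **out** | in |
| 50 | no | **out** | **out** | in |
| 51 or 70 | yes | **out** | in | in |
| 51 or 70 | no | in | in | in |

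Replacing *with no* by *with or without* closes the larger gap but still leaves age 50 out. Moving the boundary as well closes both.

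**4. Does another section repair it?** Section 5.4 does not exclude people over 50 with risk factors, but it does not admit them either. Sections 5.2 and 5.6 describe all adults over 18 using the hospitals, without saying how 5.3 is to be read. Section 2 reports a national follow-up conclusion on the need to "encourage screening in the population over 50 years of age and according to risk exposure", which points to a wider intent but is not an eligibility rule. Section 4.1 has no age limit. No section says that the older route applies regardless of risk factors.

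**5. A hint from the list itself.** One listed factor is transfusion before 1996. The reference list carries a March 2023 access date. Assuming enrolment in 2023 or later, anyone under 50 was born in 1973 or later and was at most about 22 at the end of 1995 (1995 − 1973 = 22). Confined to under-50s, that item would miss everyone transfused at older ages, which suggests that the list was not meant for younger adults only.

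**6. Consequence for section 5.10.** Under the literal rule, entrants by the age routes fall into two groups: over 50 with no listed factor, and under 50 with at least one. In a pooled chi-square test of, say, injecting drug use, the exposed are all under 50. The unexposed are a mixture of under-50s with other factors and all of the over-50s. The test then mixes the effect of the factor with that of age. Among under-50s, each single factor still varies and can be compared.

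**The case against.** The strongest reply is that nobody would apply the rule literally. The stem and the first item make sense together only if being over 50 qualifies by itself, even with no other factor. The source population is hospital users, and the list includes medical or dental interventions in care settings, so a literal older route could be nearly empty. The wording also reads like a translation in which *even without* became *with no*. This is a fair argument about intent and is probably right. It does not remove the point, because the written rule says something else and no section corrects it.

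It is also fair to say that sections 5.2 and 5.6 define a source population and frame, which are normally wider than eligibility, and that the statement in section 2 summarises another body's report. The conflict therefore rests mainly on the objective in section 4.1. That hospitals would diverge is a possibility, not something the documents show.

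A reader might infer three stronger things that the documents do not support.

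- *That age and risk factors could never be separated.* A complete tie holds only for a composite of any listed factor against none, which section 5.10 does not plan. Single factors vary among under-50s, so restriction to that age group works. Sex between men is recorded in Table 1 but is not on the 5.3 list, so it can vary among over-50s too.
- *That a countable number of participants aged 50 would be missing from the sample.* Section 5.7 recruits until the size is reached, so ineligible patients are replaced, and no age distribution is given.
- *That every at-risk patient of 50 or more is shut out.* The reinfection route has no age limit.

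**Conclusion.** The point holds as a defect of a stated eligibility rule. As written, people over 50 with a listed risk factor have no age route and can enter only as suspected reinfections. That conflicts with an objective framed around patients with risk factors at any adult age. Followed literally, the rule removes most of the older at-risk group, confines comparisons of listed factors to under-50s, and makes pooled chi-square tests mix age with risk status.

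The share of patients affected cannot be computed, because the documents give neither the age structure nor the frequency of risk factors. The sample size is unaffected. The gap at age 50 assumes completed years, which fits how age is recorded. If over 50 means past the 50th birthday, that gap nearly vanishes and the larger one remains. If all sites already apply the inclusive reading, the harm is limited to a protocol that does not describe what was done.

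**What to change.** Reword section 5.3 so that the routes meet and match section 4.1, for example: (a) aged 50 years or older, with or without a listed risk factor; or (b) over 18 and under 50 years, with at least one listed risk factor. Keep the suspected-reinfection route as it stands. The stem should then say that one of the routes must be met, since age alone is not a listed exposure. Give all seven hospitals the same written instruction, and state from when it applies if enrolment has begun.

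The cost is a short wording amendment and a site notice, with no added procedures and no change to the 1,151 per institution. The rewording does not by itself remove confounding by age: under-50s without a listed factor are still not enrolled, so crude risk-factor comparisons should be read with that in mind.
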